## 1 PROTOCOL SYNOPSIS

Study Title	Evaluation of the Safety and Clinical Performance of the Gen 2 Connected Catheter – Wireless Urinary Prosthesis for Management of chronic Urinary Retention
Short Title	FREEDOM Study
Study Sponsor	Spinal Singularity, Inc. (San Clemente, California, USA)
Protocol Number	CIP-0002 (formerly ES-NIH-01)
Study Objective	The objective of this study is to evaluate the safety and essential performance of the Gen 2 Connected Catheter in males with chronic Urinary Retention, both in a clinical setting and an extended period of home use. This is a non-significant risk (NSR) study.
Study Design	Multi-center, single-arm NSR study.
Estimated Study Duration	12 months
Investigational Device	Gen 2 Connected Catheter System and Accessories
Proposed Indications for Use	The Gen 2 Connected Catheter is a replaceable urinary prosthesis that is intended for use in male patients (subjects) 18 years of age or older who have impaired bladder emptying due to chronic Urinary Retention, and who are capable of operating the device in accordance with the provided instructions for use, or who have trained caregivers capable of doing the same. The device must be replaced every 7 days (or less).
Number of Subjects	The number of subjects to be enrolled in the study (ITT) as defined by EN ISO 14155; is 36 subjects. Of these, it is expected only 24 of the subjects will be found to meet the basic eligibility criteria to be tested for device tolerability screening.  Assuming a 33% dropout after the device tolerability screening, the final number of evaluable subjects required is a minimum of 16 subjects.
Duration of Study and Follow-up	The study will be divided into 3 phases after the Eligibility Screening. Each subject will be in the study for a total of 7 weeks. 
 
1. Device Tolerability Screening – up to one week of Gen 2 Connected Catheter use
 
2. Test – 4 weeks of Gen 2 Connected Catheter use
 
3. Follow-up – Phone screen for AE for 2 weeks
 
 During each phase, there will be weekly appointments to evaluate the subjects and device performance.

Study Population	Adult males with chronic Urinary Retention
Study Sites	Up to 4 sites in the USA
Inclusion Criteria	
 
1. Males <math>\geq 18</math> diagnosed with chronic Urinary Retention
 
2. Must be clinically suitable and capable of safely managing bladder using an intermittent voiding or indwelling strategy             
 
a. Must have stable urinary management history as determined by the Investigator OR:
 
b. Must have urodynamic profile suitable for the Gen 2 Connected Catheter (including bladder capacity <math>\geq 200\text{mL}</math> without uninhibited bladder contractions)
 
 
 
3. Subject's lower urinary tract anatomy must fall within the ranges serviceable by the Gen 2 Connected Catheter device, as specified in the Investigational Device Instructions For Use.
 

Exclusion Criteria	
 
1. Active symptomatic urinary tract infection, as defined in this clinical investigation protocol (subjects may receive the device after UTI has been treated)
 
2. Significant risk profile or recent history of urethral stricture (e.g. stricture within past 90 days)
 
3. Significant risk profile or recent history of clinically significant (uncontrolled) autonomic dysreflexia
 
4. Significant intermittent urinary incontinence (between catheterizations)
 
5. Uninhibited bladder contractions and/or Vesicoureteral reflux that is not reliably controlled with medication or alternate therapy (e.g. Botox injection)
 
6. Pre-existing urinary pathologies and/or morphological abnormalities of the lower urinary tract or bladder (assessed during in-depth medical screening, including cystoscopy and urine analysis)             
 
a. Urinary tract inflammation or neoplasm
 
b. Urinary fistula
 
c. Bladder diverticulum (outpouching) <math>> 5\text{cm}</math> in size
 
d. Chronic pyelonephritis (secondary to upper urinary tract infection(s) within past 6 months)
 
e. Impaired kidney function or renal failure
 
f. Active gross hematuria
 
g. Active urethritis
 
 
 

	
h. Bladder stones
 
7. Dependence on an electro-magnetic medical implant (e.g. cardiac pacemaker or implanted drug pump) or external device
 
8. Any unsuitable comorbidities as determined by the Investigator or complications related to use of certain medications
 
9. Any physical or cognitive impairments that diminish the subject's ability to follow directions or otherwise safely use the Gen 2 Connected Catheter System
 
10. Catheter Assessment Tool screening yields unacceptable results

Primary Efficacy Endpoint	
Primary efficacy: Post-void residual urine volume (PVR) with the use of the Connected Catheter
 
A subject is considered a responder to the treatment if a minimum of 80% of their PVR values met the following criteria
 
PVR is <math>\leq</math> 50 mL OR
 
PVR is <math>\leq</math> baseline PVR with the standard of care catheter
 
If a subject drops out before the conclusion of the study after passing the Device Tolerability Screening, their PVR data will still be included in the primary analysis.

Primary Safety Endpoint	Rate of device related SAE
Secondary End Points	
 
1. Successful device insertion, anchoring, and removal
 
2. Successful sealing of the catheter valve
 
3. Quality of life improvement as measured by SCI-QOL Survey
 
4. UTI occurrence rate
 
5. Lower Urinary Tract injury rate
 

Study and Data Management	
Spinal Singularity, Inc.
 
[name]
 
[name]
 
[contact]
 
Fax: + 1 [contact]

Study Safety Monitor	
[name], MD,
 
Professor of Urology and Radiology Chairman,
 
Department of Urology

	University of California, Irvine
--	----------------------------------

## 2 LIST OF ABBREVIATIONS

Abbreviation	Definition
AE	Adverse Event
AD	Autonomic Dysreflexia
ASIA	American Spinal Injury Association
BPH	Benign Prostatic Hyperplasia
CAT	Catheter Assessment Tool
CAUTI	Catheter Associated Urinary Tract Infection
CIC	Clean Intermittent Catheterization
CFU	Colony Forming Units
CRA	Clinical Research Associate
eCRF	Electronic Case Report Form
EC	Ethics Committee
EDC	Electronic Data Capture
FDA	Food & Drug Administration
HAI	Healthcare Acquired Infection
IC	Informed Consent
ICF	Informed Consent Form
IR	Insertion / Removal
IFU	Instructions for Use
IRB	Institutional Review Board
ISO	International Organization for Standardization
ITT	Intent to Treat Population
LUT	Lower Urinary Tract
NIDRR	National Institute of Disability and Rehabilitation Research
PVR	Post-Void Residual Volume
SAE	Serious Adverse Event
SADE	Serious Adverse Device Event
SCI	Spinal Cord Injury
SCI-QOL	Spinal Cord Injury Quality of Life
UADE	Unanticipated Adverse Device Effect
USADE	Unanticipated Serious Adverse Effect
UTI	Urinary Tract Infection

### 3 INTRODUCTION AND BACKGROUND

#### 3.1 Chronic Urinary Retention

Urinary retention is a condition in which an individual is unable to fully empty their bladder from urine. While urinary retention is not a disease, it can be a symptom of many other health issues in both males and females. Urinary retention presents itself in both acute and chronic cases. Acute Urinary Retention is sudden and can be extremely painful.

Chronic Urinary Retention develops over time and is the persistent inability to completely empty the bladder resulting in elevated post-void residual (PVR) volumes. Chronic Urinary Retention generally occurs over a long period and is typically not painful. The causes of chronic Urinary Retention can be categorized as obstructive, infectious/inflammatory, neurologic, pharmacologic, or other. Table 3-1 gives examples of these categories.

**Table 3-1: Examples of Causes of Chronic Urinary Retention**

Category	Examples
Obstructive 	Benign prostatic hyperplasia (BPH) Meatal stenosis Paraphimosis Penile constricting bands Phimosis Prostate cancer Urethral stricture
Infectious or Inflammatory 	Guillain-Barre syndrome Balanitis Prostatic abscess Prostatitis Herpes simplex virus
Neurological 	Spinal cord injury Intervertebral disk disease Spinal stenosis Spinal bifida occulta Stroke Multiple sclerosis

Category	Examples
	Diabetes mellitus
Pharmacological 	Anticholinergics Tricyclic antidepressants Anti-psychotics Antispasmodics Antihistamines, NSAIDs Muscle relaxants Opioid analgesics Amphetamines
Other	Trauma Post-operative complications Psychogenic conditions

Common methods to manage Chronic Urinary Retention from a physiological standpoint include medication and catheterization. In some cases, surgical intervention may be required, but are invasive and are only used as a last resort. Medications such as alpha-blockers have been effective in both males and females, but have many possible side effects such as:

- Dizziness
- Fainting
- Headaches
- Lightheadedness
- Low blood pressure
- Rash or itchiness of the skin
- Nausea
- Swollen legs or ankles.
- Tiredness, weakness or feeling lethargic.
- Sleep disturbance.
- Tremor.
- In some cases, erectile dysfunction in males

[figure not shown]
Because of these side effects, catheterization is often used as an alternative to manage chronic Urinary Retention . Both intermittent catheterization and the use of indwelling catheter are valid treatment options, although indwelling catheters are typically only used when long-term care is needed. With both methods of catheterization there is risk of urethral injury and UTI with the rate of occurrence for UTI being higher with the use of indwelling catheters. Indwelling urinary catheters also require the subject to have a drainage bag with them to collect the urine which can negatively affect the subject's quality of life. Traditional indwelling catheters are typically fixated within the bladder with an inflatable balloon. If the balloon bursts it cause bladder injury and the catheter will migrate or fall out of the patient completely. Additionally, the catheter often extends outside of the body which interferes with sexual activity.

The Gen 2 Connected Catheter aims to bring an improved experience for patient's requiring catheterization. The Gen 2 Connected Catheter does not need to be replaced as often as catheters used for intermittent catheterization but does not remain in place as long as typical indwelling urinary catheters. It also provides increased convenience over indwelling urinary catheters as the device does not protrude outside of the body, allowing for sexual activity, and does not require the subjects to carry a drainage bag. It also does not have a balloon as it uses two anchoring features located in the urethra and the bladder. The Gen 2 Controller allows the subjects to control voiding. Additionally, the increased frequency of replacement versus indwelling catheters may decrease the occurrence of UTI in the subjects versus traditional indwelling catheters that may be left in the body for up to 29 days.

## 4 INVESTIGATIONAL DEVICE DESCRIPTION

To address the many drawbacks of current standard-of care urinary catheters, Spinal Singularity, Inc. has developed the Gen 2 Connected Catheter System and Accessories. The Gen 2 Connected Catheter System consists of the Gen 2 Connected Catheter (hereafter referred to as the Connected Catheter), the Gen 2 Insertion / Removal Tool (hereafter referred to as the IR Tool) and the Gen 2 Controller (hereafter referred to as the Controller). The Gen 2 Catheter Assessment Tool (hereafter referred to as the CAT) is an optional accessory for clinicians to support initial and continued determination of whether the Connected Catheter may be an option for a suitable potential patient. The Connected Catheter (Figure 4-1) is a fully internal, indwelling urinary prosthesis designed for improved bladder management in males with urinary retention disorders requiring catheterization. The Connected Catheter is a sterile, disposable, extended-use device that resides fully internally to the male lower urinary tract (urethra + bladder neck) for an intended use life of up to 7 days per Connected Catheter.

In contrast to indwelling Foley and clean intermittent catheters, the Connected Catheter enables both natural bladder filling and convenient, voluntary voiding by the user, without the need for external drainage apparatus or frequent self-catheterization. Instead, the user initiates voiding by placing a wireless hand-held Controller near the magnetic valve in the base of the penis. When activated, the Controller will open the valve and actively pump urine from the bladder, then seal once voiding is complete. The Connected Catheter is retained in place by using varying diameters to provide anchoring at different locations in the urethra. The Connected Catheter is designed to be easily inserted and removed either by a clinician, caregiver, or the user himself, using a sterile, single-use, IR Tool.

**Figure 4-1: Overview of System**

The Gen 2 Connected Catheter System and Accessories are manufactured by Spinal Singularity, Inc. Each device (Connected Catheter, IR Tool, Controller and CAT) are manufactured and labeled in accordance with Spinal Singularity Inc.'s Quality Management System procedures. These procedures are in compliance with applicable FDA regulations and in conformance with ISO standards for Device Traceability and Identification. In doing so, Spinal Singularity, Inc. and Research Staff will maintain full traceability of every investigational device throughout the duration of the study using lot numbers and serial numbers. Accountability of all investigational devices will be maintained by the clinical research staff and Spinal Singularity, Inc. will also track serial numbers of each investigational device utilized in the study.

All portions of the Gen 2 Connected Catheter System and Accessories will contact the subject's body in some fashion for a period of time. To maintain subject's safety, thorough testing of each device has been conducted to ensure appropriate levels of electrical safety, biocompatibility and

sterility. Although the requirements for each device are different, test results have shown that the product meets applicable FDA regulations and ISO standards.

#### 4.1 Principles of Operation

The basic principle of the Connected Catheter is to allow the subject to void their bladder using a wireless Controller and a magnetic valve. A summary of the treatment is provided below only as an overview. The IFU should always be followed and if different from this section, the IFU should be followed.

1. Using the IR tool and lubrication, the Connected Catheter is inserted in the urethra. The valve (end of the Catheter) should be positioned near the scrotum before the IR tool is removed.
2. To urinate, locate the valve by feeling with a hand. Position the Controller near the valve – the end of the valve should align with the blue line on the Controller.
3. Press and hold the button on the Controller for 3 seconds to open the valve and urinate. The Controller should be kept in line with the valve as much as possible.
4. When the bladder has been emptied, re-align the Controller with the valve and press the button on the Controller and move the Controller towards the tip of the penis. This will close the valve.
5. Empty the receptacle if necessary.

### 5 PROPOSED INTENDED USE

The Gen 2 Connected Catheter is a replaceable urinary prosthesis that is intended for use in male patients (subjects) 18 years of age or older who have impaired bladder emptying due to chronic Urinary Retention, and who are capable of operating the device in accordance with the provided instructions for use, or who have trained caregivers capable of doing the same. The device must be replaced every 7 days (or less).

The Gen 2 Connected Catheter System is intended for use by prescription only.

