## 8.3 Test Phase

During this period, the subjects will use the Connected Catheter to manage their chronic Urinary Retention. The subjects will remove the device themselves under supervision of a trained clinician. A new Connected Catheter will be inserted by the subjects under the supervision of a

trained clinician. There will be weekly follow-ups during this period to complete assessments as outlined in Table 9-2.

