### **9.2.7 Clinic Assessment Completion and Subject Discharge**

Prior to discharge, the subject will complete the Connected Catheter User Experience Survey. If the Connected Catheter fulfills the objective performance criteria for all areas of essential performance (insertion, voiding and anchoring) then the subject will leave with their current Connected Catheter inserted, be scheduled for the next office appointment (at Day  $7 \pm 1$ ), and will be discharged from the Study Site for the Device Tolerability Screening Phase.

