## **9.3 Device Tolerability Screening**

During the Device Tolerability Screening, subjects will use the Connected Catheter to manage their chronic Urinary Retention. The duration of Tolerability Screening will be up to 7 days after the patient has had the first device inserted. The purpose of this screening is to ensure that the subjects can both tolerate the device and learn how to operate it properly. Any subject that experiences significant discomfort or cannot demonstrate proficiency in the operation of the device (or does not have a caretaker) will not proceed to the test phase of the study. Patients that are able to successfully use the device for up to 7 days and wish to continue the study will progress to the test phase. The data collection during the Device Tolerability Screening is identical to the data during the Test Phase. The subjects will be trained to manage his bladder using the Connected Catheter via the Controller on an intermittent voiding strategy. Instructions for Use (IFU) will be provided to the subject regarding how to properly use the Connected Catheter. The same assessments used in the Test Phase will be done at the end of the Device Tolerability Screening phase.

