## **9.4 Test Phase**

The Test phase will require three (3) Exchange Appointments and a final Removal Appointment. Each appointment will assess PVR, voided volume, quality-of-life (QOL), and urinary tract injury, adverse events, medication, and other study assessment. Additionally, the subjects will be asked to fill out a User Experience Survey and Safety and Performance Survey and the device will be evaluated for fit, migration, placement, and removal.

At each exchange visit, the clinic research staff will follow these procedures:

1. Patient Arrival – Vital Signs and other measurements
2. Bladder Volume – Measurement using Ultrasound to ensure at least 200 mL of urine
3. Patient empties bladder – PVR volume measurement using Ultrasound
4. Patient removes Connected Catheter
5. Patient waits for bladder to fill – additional surveys completed
6. Patient inserts new Connected Catheter and bladder emptied – PVR volume measured
7. Patient Departure

For the final device removal visit the clinic research staff will follow these procedures:

1. Patient Arrival – Vital Signs and other measurements
2. Bladder Volume – Measurement using Ultrasound to ensure at least 200 mL of urine
3. Patient empties bladder – PVR volume measurement using Ultrasound
4. Patient removes Connected Catheter
5. Patient completes all surveys
6. Patient departure

Once the patient completes the final device removal visit the patient will enter the follow-up phase.

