**Table 9-2: Schedule of Visits**

	Eligibility Screening	Device Tolerability Screening	Test Phase	Follow-Up	Unscheduled
Compliance window		<math>7 \pm 1</math> days	<math>7 \pm 1</math> days	<math>7 \pm 1</math> days	
Basic Vital Measurements	✓	✓	✓		✓
Physical Examination	✓				
Urinary Tract Visual Examination	✓				

	Eligibility Screening	Device Tolerability Screening	Test Phase	Follow-Up	Unscheduled
(cystoscopic, if necessary)					
Catheter Assessment Tool (CAT) Evaluation	✓				
Medical History	✓				
UTI Assessment including Urinalysis	✓	✓	✓		
PVR Measurement	✓	✓	✓		
Voiding Volume Measurement	✓	✓	✓		✓
SCI-QOL Bladder Management Survey	✓	✓	✓		
Current Catheter Experience Survey	✓				
Medication(s) used	✓	✓	✓		✓
Connected Catheter User Experience Survey		✓	✓		
Connected Catheter Safety and Performance Survey		✓	✓		
USQNB-IC Survey	✓	✓	✓		
Connected Catheter Weekly Assessment Includes: 
 
• Device Insertion Assessment
 
• Device Sizing
 
		✓	✓		

	Eligibility Screening	Device Tolerability Screening	Test Phase	Follow-Up	Unscheduled
and Positioning					

 
• Catheter Sealing
 
• PVR Measurement
 
• Voided Volume
 
• Catheter Migration
 
• Urethral Injury Assessment
 
• Device Removal Assessment
 
• QOL Survey
 
					
Follow-Up Phone Screening for Potential AE				✓	
Adverse event(s) review		✓	✓	✓	✓
There are weekly appointments during the Test Phase and weekly phone calls during the Follow-Up Phase					

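### The 7 ± 1 day visit window lets a catheter stay in for 8 days, although the protocol limits wear to 7 days or less

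*Combined protocol and SAP*

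**What the plan says.** The wear limit appears in three places. Section 5 states "The device must be replaced every 7 days (or less", the synopsis repeats this under the proposed indications, and Section 4 describes the device as meant "for an intended use life of up to 7 days per Connected Catheter". None of the three allows a tolerance.

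The visit schedule is in Table 9-2, where the row labelled "Compliance window" reads 7 ± 1 days for Device Tolerability Screening, the Test Phase and Follow-Up alike.

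The visit is also when the catheter comes out. Section 8.3 says "The subjects will remove the device themselves under supervision of a trained clinician". Section 9.4 lists "Patient removes Connected Catheter" as a step of both the exchange visit and the final visit. It also fixes the number of visits: "The Test phase will require three (3) Exchange Appointments and a final Removal Appointment".

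For the first catheter, Section 9.2.7 sends the subject home with the device in place, to "be scheduled for the next office appointment" at Day 7 ± 1. Section 9.3 says "The duration of Tolerability Screening will be up to 7 days after the patient has had the first device inserted".

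**The concern.** Wear time in this study is the interval between two visits, so the upper edge of the visit window is also the longest wear the schedule accepts. That edge lies beyond the stated use life. A site that keeps every visit inside the window can still leave a device in place longer than the protocol permits, and the protocol does not say which rule governs.

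Two things are at stake:

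- **Subject exposure.** A subject may wear an indwelling device past its use life while the visit counts as compliant. Section 14.8.3 gives a missed visit window as an example of a deviation but does not mention wear time, so such an exchange may not be flagged.
- **The data.** Under Section 9.4 the first residual volume at an exchange visit, and the only one listed for the removal visit, is measured before the worn catheter is taken out. On day 8 that reading describes the device outside its proposed use, yet it counts toward the subject's 80% responder rule. The same applies to secondary endpoints such as sealing, UTI and lower urinary tract injury, which Section 8.6 ties to possible labelling claims.

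**Working it through.** No power or sample size formula applies. The check is arithmetic on the visit window.

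**Inputs**

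- Wear limit: 7 days (synopsis, Sections 4 and 5).
- Visit window: 7 ± 1 days, that is 6 to 8 (Table 9-2).
- Test Phase visits at which a catheter is removed: 3 exchanges + 1 final removal = 4 (Section 9.4).

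**Wear per catheter, window counted from the last insertion**

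- Longest compliant wear = 7 + 1 = 8 days.
- Excess = 8 − 7 = 1 day; 1/7 = 14%.
- Periods affected: between 0 and 4 of 4 per subject. The documents give no expected distribution of visit days.
- Total Test Phase wear with every visit at the upper edge = 4 × 8 = 32 days, against 4 × 7 = 28.

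**Wear per catheter, window counted from fixed study days**

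Table 9-2 does not say what the window is counted from. If visits are due at fixed study days (7, 14, 21 and so on, each ± 1), a visit one day early followed by one a day late gives 7 + 1 + 1 = 9 days. That is 2 days over the limit (2/7 = 29%). Eight days is thus the smaller of the two readings.

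**Tolerability period**

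Section 9.2.7 allows a return on Day 8. If insertion is Day 0, wear is 8 − 0 = 8 days, which conflicts with Section 9.3. If insertion is Day 1, wear is 8 − 1 = 7 days and there is no conflict. The protocol does not define the convention. With insertion as Day 0 and every visit at the upper edge, total wear over five catheters is 5 × 8 = 40 days, against 5 × 7 = 35.

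**Efficacy readings exposed**

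Section 9.4 lists two residual volume measurements at each exchange visit and one at the removal visit: 3 × 2 + 1 = 7. Of these, 3 + 1 = 4 are taken with the worn catheter still in place. So up to 4 of the 7 listed Test Phase readings could come from a device past its use life.

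**Is there a day-7 backstop?**

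Section 7.2 gives subjects an IR Tool so that the catheter can be taken out if the need arises. It does not require removal at day 7 when the visit is set for day 8, and no other section does.

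**The case against.** The strongest reply is that a visit window and a wear limit are separate rules that can both be met. Visits on days 6 and 7 satisfy each, and nothing tells a site to leave a device in for 8 days. This is true, but it describes a window whose upper edge was not trimmed to the limit. A day-8 visit is still classed as on time.

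A second reply is that over-wear would be caught. The examples in Section 14.8.3 are open-ended, and Section 15.1.1 lets monitors check that devices are used according to the protocol and the Instructions for Use. This has some weight, and it is why the claim is only that a day-8 exchange may go unflagged. The monitoring check is optional, however. Section 15.1.1 anticipates at least one monitoring visit per site, once follow-up there is complete, which is after the exposure.

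Third, the Instructions for Use are not among the documents and may set a stricter rule. That cannot be checked, and a stricter rule there would leave the protocol's own window and limit in conflict.

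Fourth, nothing shows harm on an eighth day, and the point does not touch the primary test, alpha, power or sample size. Both statements are correct. They limit the weight of the point but do not remove it, since nothing in the documents shows that an eighth day is safe either.

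**Conclusion.** The concern holds. A Test Phase visit that complies with Table 9-2 can breach the wear limit in the synopsis and Sections 4 and 5, and no provision requires removal by day 7.

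The excess is up to 1 day per wear period (14%) in 0 to 4 of the 4 Test Phase periods, assuming the window runs from the last insertion. A single period could reach 9 days if the window runs from fixed study days. The tolerability period is a fifth only if insertion is Day 0. The clinical effect cannot be estimated from the documents.

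This should be corrected because it bears on subject exposure and on whether the data reflect the proposed use. It does not alter the statistical test.

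**What to change.** In Section 9.2.7 and Table 9-2, set the exchange and removal window to 7 (−1/+0) days, counted from the last insertion. Stating the anchor rules out the 9-day reading and settles the Day 0 question for the tolerability period. Record the insertion and removal date of each catheter, and log any wear beyond 7 days as a protocol deviation.

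The cost is small: wording in two places, and two date fields per catheter if the eCRF does not already hold them. Scheduling tightens from 3 acceptable days (6, 7, 8) to 2 (6, 7). Total Test Phase wear would run from 4 × 6 = 24 to 4 × 7 = 28 days. Counted from the last insertion, the current window already permits 24, so only the upper end changes, from 32 to 28.

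A window of 6 ± 1 days would keep 3 acceptable days (5 to 7) and also respect the limit. However, total wear could fall to 4 × 5 = 20 days, well short of the 4 weeks of use planned in the synopsis. The 7 (−1/+0) window is the better choice.
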